- The entire surface area of every margin of the outer final surface should be sampled. MarginProbe sampling shall be evenly spread, usually 5-8 points per margin, depending on the specimen size, or up to 12 points per margin in larger specimens.
- Each single site reading is performed as follows: The surgeon positions the hand-piece tip perpendicular to the relevant tissue section. The system automatically performs a full cycle of measurement. The site result, "Positive" or "Negative", is displayed on the monitor in real time along with audio indication.
- Once the device has been applied to all margins, all margins indicated by the MarginProbe as positive (a margin is indicated positive if there is one or more positive readings on it) should be shaved from the cavity.
- Additional cavity shavings performed based on device use will be documented.
- If the shaving is taken after the x-ray, take the shaving from the outer final surface.

Intraoperative Imaging assessment - both arms of the trial

- If part of routine practice, specimen imaging by ultrasound or radiography should be performed.
- Results of imaging assessment will be documented.
- Additional cavity shavings performed based on intraoperative imaging assessment will be documented.

Concomitant patient management

• Use of saline and/or ultrasound gel and/or local anesthetic on the main ex vivo lumpectomy specimen before performing the MarginProbe measurements is precluded. Sterile water can be used instead.

Additional lumpectomy cavity shavings handling - both arms of the trial

- All lumpectomy cavity shavings should be appropriately oriented, marking with a suture the new margin and clearly noting for pathology the orientation of the shaving relative to the main ex-vivo lumpectomy specimen.
- The shaving name as reported by the surgeon to the pathologist shall be documented
- If a lumpectomy cavity shaving encompasses more than one margin in one main ex-vivo lumpectomy specimen, this should be documented by the surgeon and mentioned in the pathology report.
- If more than one shaving is taken from the same face, it shall be documented if the shaving is the outermost cavity shaving or not.

Conclusion of procedure - both arms of the trial

- The procedure will be concluded in the routine practice.
- All tissue removed during the initial lumpectomy procedure will be submitted for routine permanent histology analysis.

Surgical Principles – WLE for palpable or impalpable lesions:

These may be either through the UK screening programme from the Nightingale Centre or lesions on mammograms requested for other reasons. Ultrasound guided surgery or needle localisation surgery is used. In the former the surgeon removes the area of breast tissue at a depth calculated by the scan, consistent with the scan findings. At needle localisation a volume of tissue is removed together with the wire.

- 1 In both cases liga-clips must orientate the specimen. One clip is used superiorly, two clips laterally and three inferiorly if this is written fully on the card then the radiologist will be able to ascertain the orientation of the specimen. It must also be recorded on the operation note.
- 2 The biopsy cavity site must be orientated with 4 ligaclips, superiorly, inferiorly, medially, laterally. This is important for the planning of adjuvant radiotherapy.
- 3 The excised specimen must be weighed and recorded in the operation note
- 4 Shavings must be taken from the adjacent breast tissue and sent separately. The shavings may have a sutures placed on the biopsy (inner) cavity surface to allow the pathologist to orientate the shaving itself. Ligaclips cannot be used as they would interfere with the device.
- 5 All impalpable lesions must be visualized radiologically by the operating surgeon on the intheatre X-Ray machine. The specimen should be radiographed in two perpendicular planes for a radiological assessment of the completeness of excision. A comment on the completeness of excision based on the intraoperative image must be made in the operation note by the surgeon. If the biopsy is undertaken for microcalcification a comment must be made in the operation note relating to the presence of microcalcification in the X-Ray image of the excision specimen. Any concerns should be discussed with a Consultant intraoperatively.
- 6 It is mandatory to obtain an intraoperative X-Ray image of a radiologically guided WLE.
- 7 It is expected that intraoperative images of WLE specimens in palpable cancers will also be obtained. It is not routinely required to obtain an intraoperative images of biopsy cavity shavings but this may be helpful in cases where the main specimen radiograph does not show the malignancy.
- 8 Intraoperative images should be electronically sent to Radiology for formal radiological assessment and to inform the MDT discussion of the case and complete radiological assessment of the lesion.
- 9 The patient should remain anaesthetised until confirmation of removal of the targeted lesion.
- 10 If cytology or corecut biopsy has produced malignant cells a therapeutic biopsy may be undertaken. If not, a diagnostic biopsy weighing less than 20g must be carried out. Wherever possible a therapeutic rather than a diagnostic operation should be done.
- 11 Axillary node surgery should be carried out in association with localisation surgery only if a diagnosis of invasive carcinoma has been proven preoperatively.
- 12 It is the responsibility of the operating surgeon to ensure the pathology forms are concordant and record accurately the specimens submitted for histopathological examination. The specimens sent for histology should be recorded in the operation notes as stated in the Royal College of Surgeons publication "Good Surgical Practice".
- 13 The operation note should record the specimen weight and whether or not the specimen was x-rayed and the lesion was present in the specimen.

Fidelity checks will be instigated to ensure telephone randomisation time fits with theatre records and probe use.

Intraoperative surgical resection correctness using the probe will be checked between probe results recorded on the console and resection specimens.

Please see Appendix B for further information about the MarginProbe Device.

Intraoperative

General:

- Use of the device will take place during a lumpectomy procedure only in patients randomized to the "Device" arm.
- The console will be set-up in the OR and turned on. This is in preparation for the randomization phase, and so as not to lose time if the patient is randomized into the "Device" arm.

Pre-Randomization:

- The main ex-vivo lumpectomy specimen will be excised in the surgeon's routine surgical manner.
- All main ex-vivo lumpectomy specimens will be suture oriented (using standard of care techniques), so as to uniquely define the aspects of the specimen relative to the body (lateral, medial, superior, inferior, deep, anterior; see also figure below). The orienting suture (clip, or other similar means) should be placed in the centre of the margin, as perceived by the surgeon.

• In all main ex-vivo lumpectomy specimens, the borders of each of 6 margins should be marked by the surgeon by thin ink markings (see figure below), for further assist in pathology assessment.

- Intraoperative assessment by visual inspection and palpation will be performed by the surgeon.
- Additional lumpectomy cavity shaving is performed by the surgeon, as deemed necessary, based on this intraoperative assessment.
- Lumpectomy cavity shavings performed based on visual inspection and palpation shall be documented.

Please see Appendix B for further information about the MarginProbe Device.

MarginProbe Schedule of Assessments

2.1					
			1 month	3 months	9 months
	Baseline/	Operative	post	post	post
Assessment	screening visit	visit	surgery	surgery	surgery
Informed Consent	x				
Eligibility criteria	х				
Demographics	х				
Baseline characteristics	x				
Relevant Medical History	x				
Procedural characteristics		x			
Intraoperative imaging use		x			
Pathology assessment		x			
FACT-B, HADS, EQ5D, SABIS					
Questionnaires	X		X (by post)	X (by post)	X (by post)
Randomisation		x			
Photographic measurements	x				x
Adverse events assessed		x	x		
Health Economic Diaries			X (by post)	X (by post)	X (by post)

NB: Adverse events and Serious Adverse events should be recorded, as appropriate, at all points of contact.

4. Data Analysis and Statistical Considerations

Sample size: The ABS 2011 Audit[1] found the average re-excision rate for DCIS is 30% and that for invasive cancers is 25%. It is estimated that approximately 20% of recruited patients will have DCIS and 80%, invasive cancer. The estimated average re-excision rate for the whole study group is 26%. Specialist Centres are expected to have a slightly lower re-excision rate, if we assume a 25% re-excision rate in the control arm and predict that the device will give a 50% reduction in the re-excision rate (i.e. to 12.5%), it is estimated that 219 patients will be required to be recruited in each group (90% power using a simple chi-square test with continuity correction). It is proposed to recruit 230 per group to allow for drop-out and loss to follow-up.

With this number of patients, the study would have 80% power to detect a 44% relative reduction from 25% to 14% in re-excision rate and a 50% relative reduction from 20% to 10% in re-excision rate.

This number of patients would also lead to 90% power to detect differences in TOI of 4.5 or more between the two groups and 80% power to detect differences in TOI of 3.9 or more (using an estimated SD of 15 from the ALMANAC trial and a simple two-sample t-test with the conventional 5% significance level).

The Breast Screening Centres selected treat over 2,600 cancers each year of which over 1,800 will require BCS. In this group of patients, 50% agree to participate in treatment trials, however, we would expect a higher rate as this trial does not involve patients having to take additional trial medication and similar non-medical intervention trials have recruited up to 60% in Manchester. Thus we expect to recruit the required number of 460 patients within one year from the participating centres. We would not expect loss of population due to death as these patients will be fit for anaesthetic and survival is in excess of 98% at 10 years.

Randomisation: Allocation of patients to either standard procedure or the use of the Margin Probe device in a 1:1 ratio will be made using the method of simple permuted block randomisation (with random block sizes) .Patients will be individually randomised by telephone via the MAHSC-CTU.

Baseline data: Patient characteristics will be summarised using numbers and percentages for qualitative data, medians and ranges for ordinal qualitative data and non-Normal continuous data, and means and standard deviations for Normally distributed continuous data. Normality will be assessed by inspection of distribution graphs and skewness/kurtosis statistics.

Primary Endpoints: The re-excision rate (at least one further surgical re-excision operation by 9 months) between the two groups will be compared initially using the simple chi-square test followed by logistic regression analysis (to adjust, if necessary, for any potential confounding factors e.g. Centre; DCIS vs invasive). Total numbers of re-excisions will be compared using generalised linear models with Poisson or Negative Binomial regression. The percentage of patients with excision margins \leq 1 mm after one BCS procedure will be compared using logistic regression analysis.

Secondary Endpoint: Tissue weight excised will be compared initially between the two groups using the simple t test followed by linear regression analysis (to adjust, if necessary, for any potential confounding factors e.g. Centre; DCIS vs invasive). Ordinal regression will be used to compare the cosmetic evaluation scales.

Quality of Life assessments: QoL will be measured in each group by using validated selfcompletion disease specific and generic instruments, FACT-B[11],HADS[12] and EQ5D for healthrelated utility, together with the body image scale of SABIS[16]. These will be administered at baseline (pre-surgery) and by postal follow-up at 1,3,9 months post-surgery, permitting calculation of Trial Outcome Index (FACT-B TOI).). Analyses of covariance will be used to compare QOL scores between the groups at 6 months follow-up, adjusting for baseline scores and other potential confounding factors (e.g. Centre, chemotherapy use). In addition, longitudinal regression analysis, using generalised estimating equations, will be used to compare the QOL scores between groups over the whole follow-up period (1, 3 and 9 months post randomisation).

Missing data: Missing QOL data at follow-up time points will be adjusted for in the statistical analysis using multiple imputation procedures.

Statistical Approach: All analyses will be by intention-to-treat using the conventional twosided 5% significance level. The statistical software packages SPSS and STATA will be employed to carry out the statistical analyses.

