1. SUMMARY OF TRIAL

Of the 48,000 breast cancers diagnosed annually in UK, almost 60% of patients undergo breast conserving surgery (BCS). Surgical removal of the cancer aims to reduce the risk of local recurrence and patient mortality. In order to minimise the amount of tissue removed, excision up to the cancer-free area (margins) is undertaken. Further surgery following BCS is required in 25% of patients with invasive cancers with surrounding DCIS and 30% of DCIS patients because of disease found at the edges of the tissue removed.

Reducing the need for further operations benefits patients (by reducing the number of operations required, minimising anxiety) and the NHS (by realising economic benefits).

MarginProbe, a disposable probe which measures the margins of tissue removed during BCS surgery, allows the surgeon to remove further tissue during the same surgical procedure to clear any involved margins, minimising subsequent re-operations.

Four hundred and sixty patients in 6 specialist Breast Units will be randomly allocated peroperatively after BCS (and specimen radiology), by telephone randomisation, to either:

- MarginProbe assessment of the surgical specimen with re-excision of margins if required;

- Standard BCS (clinical and radiological clear margins) whereby the wound will be closed and the surgery completed (standard UK practice).

The primary aim of the study is to determine whether the MarginProbe device reduces the need for second surgical procedures (and improves margin clearance by \geq 1mm) by enabling the removal of involved margins during the same procedure.

Main outcome: number of people requiring second re-excision surgery within 9 months of their first BCS. We will also look at the impact on quality of life, cosmetic appearance and the results of laboratory assessments of removed tissues.

The health related quality of life and cosmetic appearance of the surgery (photographs of 2 views - front/side) will be compared by researchers who do not know which treatment people received.

AIM

Surgical excision of breast cancer and surrounding ductal carcinoma in situ (DCIS) aims to reduce the risk of a local recurrence and increased mortality of the patient, by excising the cancer with cancer-free margins. Surgical practice in the USA allows for examination of frozen tissue section taken during breast conserving surgery to identify involved or close cancer margins.

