TRIAL OBJECTIVES

Primary Objectives:

1. To determine if intraoperative margin assessment after excision of a cancer reduces reexcision procedures, compared to standard surgical practice by 9 months after primary surgery.2. To compare the total number of re-excision procedures required between groups and tissue weight resected after BCS, because of positive margins.

Secondary objectives:

- 1. To determine the effect of margin assessment on a) quality of life (QOL), b) cosmetic outcomes and cost-effectiveness (EQ5D).
- a) QOL in each group will be measured by using validated self-completion disease specific and generic instruments, FACT-B[11], HADS[12], health-related utility (EQ5D) and the body image scale of SABIS[13] administered at baseline (pre-surgery) and postal follow-up at 1,3,9 months post-surgery to permit calculation of Trial Outcome Index (FACT-B TOI). This assessment will permit area under the curve approach to analysis of differences between arms in QoL.[C1] Quality of life is a crucial variable if we are to understand the impact of MarginProbe, especially if the effect on re-excision rates is not of marginal significance. The effect of avoiding re-excision or mastectomy on the quality of life of women may act as a multiplier which makes the procedure worth (or alternatively not worth) undertaking even if the actual numbers of excisions and mastectomies avoided is marginal.
- b) Cosmetic evaluation, blind to randomisation assignment will be conducted at baseline and 9 months by observer using a symmetry based scale[14] and photographic measurements compared by observers blinded to randomisation. Two independent observers will use the symmetry-based ratings and undertake the photographic measurements to assess cosmetic outcomes. Inter-rater agreements will be calculated to check reliability of observations. Patient related outcomes will be measured using the Harvard Cosmesis Scale[21].

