2. BACKGROUND

Breast cancer is diagnosed in over 48,000 women per year in the United Kingdom, with at least 60-70% undergoing breast conservation surgery (BCS)[1,2]. Standard management requires BCS to achieve histologically-negative margins (>1mm circumferential clearance)[2] prior to radiotherapy because if margins are involved, the risk of subsequent local recurrence and

mortality is increased[3-6,11]. The presence of microcalcification in surrounding DCIS is a predictor of margin involvement for cancers detected by screening mammography (20-25% of new breast cancers)[3-6].

Meta-analysis shows that for every five women who develop local recurrence, one will die of breast cancer, thus prevention of local recurrence by complete surgical excision with histopathologically-clear margins after BCS has become an essential part of oncological treatment[11].

NICE guidelines for BCS advise either re-excision or mastectomy in patients where margins are involved with cancer cells after BCS[2]. Prospective data are lacking on margin width clearance required, but three retrospective analyses of margin width within large DCIS trials suggest width of 1mm clearance is sufficient[6] and a large metaanalysis of invasive breast cancer identified a 1mm margin as adequate to prevent recurrence[20]. Re-excision procedures occur 5-6 weeks after initial BCS, producing social and economic costs to the patient (reduced cosmesis, increased risk of infection and additional time off work/recovery time) and to the NHS in terms of surgical time and in-patient care.

A recent Association of Breast Surgeons Audit suggests that 16% of invasive cancers go on to require re-excision and 9%, mastectomy, after initial BCS, as well as up to 37% of non-invasive breast cancer (DCIS) because of circumferential margin involvement[1]. At least 1 in every four DCIS and breast cancer with surrounding DCIS diagnosed on core biopsy/mammotome surgery need second re-excision operations[1].

Re-excision operations on average cost £2,885 and mastectomy with breast reconstruction costs around £6,714, thus considerable savings are possible if 2nd operations are avoided.

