
A positive margin by histology is defined in this study as a margin microscopically measured and reported in the histology report to have cancer within 1 mm or less of the inked surface.

Cold ischemia time should be kept to less than 1 hour based on ASCO guidelines.

Data Collection

Each research site is responsible for maintaining source data for their trial patients in their medical notes, and for transcribing this data onto a trial specific case report form (CRF). All entries on the CRF, including corrections, must be made by an authorised member of trial staff. Research site staff will also provide trial patients with copies of the relevant questionnaires for completion at each required time-point.

Research sites will submit original completed copies of the CRF and patient completed questionnaires to MAHSC CTU, keeping a copy at site with the Investigator Site File.

Patient diaries should be returned to the Sponsor site for analysis.

Follow up and data collection; MarginProbe use starts and ends during the primary lumpectomy procedure. Thus, patient management differs between the two study arms only during the procedure. Following the procedure, pathological assessment and any other patient management aspects are identical for both study arms. The device will not be used in any repeated surgery, even in patients randomised to the "Device" arm.

Data will be collected regarding all ipsilateral breast surgical procedures and their respective permanent section histological data. Patients will be followed until evaluation of cosmetic status, performed at 6 +/- 1 month following the end of surgical treatment (either conversion to mastectomy, or the latest ipsilateral repeat lumpectomy procedure).

In the event a repeat lumpectomy procedure or mastectomy has occurred during the data collection period, additional information will be recorded in the case report form.

Data will be collected on any repeated ipsilateral breast surgical procedure, including axillary lymph node dissection (ALND), and sentinel lymph node biopsy (SLNB), including permanent histopathology data. Surgical procedures performed in the contralateral breast will be also documented.

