CTU provide relevant information to IDMC, Study Committee meetings and for the purposes of site monitoring QA/ QC of data

Database lock and providing data to the statistician for statistical report generation

Questionnaires returned to CTU CTU perform data entry and maintain missing pages log

CTU raises data queries for sites

Sites return data queries to CTU

CTU provide relevant information to the team at the University of Liverpool for analysis

Patient diaries returned to study coordinator at the Sponsor site.

Diaries received at the University of Liverpool for analysis.

Initiation Meeting and Study Training: An initiation meeting at each site will occur after relevant staff from participating sites have attended a training day where they are trained by [name] and Dune Medical Device representatives in the use of the Probe.

The CI, or an appropriate delegate, intends to visit each site when the study is due to commence there, to observe the first two patients undergoing surgery for the trial. This will ensure that the same operating procedure is used in each centre. Agreed Protocols for re-excision according to standardised margin width will also be standardised across all sites. Please see Appendix B for further information about the MarginProbe Device.

Cosmetic evaluation: The cosmetic outcome assessment will be performed using objective evaluation. The objective evaluation will be performed by two evaluators blinded to arm assignment. The evaluation will be based on pictures taken, under standardized photographic conditions, which will be conducted at baseline and 9 months (. Only the breast and torso (excluding the head and neck) will be photographed. The pictures will be provided to the lead study site electronically and all be evaluated together by clinicians who were not involved in the initial research. The scoring will be performed using a symmetry based scale[14] and photographic measurements (two views; front and side) compared by observers blinded to group allocation. The validated 4-point Harvard Breast Cosmesis Scale will be used[21]. This scale classifies the overall aesthetic results in four categories:

- Excellent Treated breast almost identical to untreated breast.
- Good Minimal difference between the treated and untreated breasts.
- Fair Obvious difference between the treated and untreated breasts.
- Poor Major functional and esthetic sequel in the treated breast

Minimizing loss to follow up

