Loss to follow up that will influence the collection of valid data for the co-primary endpoints is not expected in this study. The co-primary endpoint data is obtained during the (initial) surgery and during a period of up to two weeks following it. Additionally, this data is collected routinely as part of the subject's standard treatment. In the pivotal study there was no loss to follow-up.

Loss to follow up that will influence the collection of patient questionnaires and diaries at 1, 6 and 9 months following the end of surgical treatment, will be minimized by letters and reminder phone calls to the patients, and also by providing patients with stamped addressed envelopes.

Sites will also be provided a 3 month window in order to collect data and complete photographs for the 9 month period; these can be completed up to 12 months post-surgery.

3. Trials Procedures

Baseline/screening visit:

- Eligibility criteria
- Informed consent
- Demographics Baseline characteristics(height, weight, bra cup and band size)

- Relevant medical history
- Pre-operative information
- Disease characteristics
- FACT B +4, HADS, EQ5D and SABIS Questionnaires administered

Operative visit:

- Procedural characteristics
 - Surgery information
 - o Device use information, including failures and malfunctions
 - \circ $\;$ Lumpectomy cavity shavings performed based on visual inspection and palpation $\;$
 - Lumpectomy cavity shavings performed based on device use (Device arm only)
- Intraoperative imaging use
 - Performed (Y/N)
 - o Imaging technique
 - Imaging result (when applicable)
 - o Lumpectomy cavity shavings performed based on intraoperative imaging assessment
- Pathology
 - Tumour type
 - o Margin status main ex-vivo lumpectomy specimen and lumpectomy cavity shavings
 - o Margin depth
 - Specimen dimensions
- Adverse events and Serious Adverse Events

Follow up visits (month 1, 3 and 9):

• FACT B +4, HADS and EQ5D Questionnaires and Patient Diary Cards Administered

MarginProbe Device

In patients randomised to the device arm, the MarginProbe will be used after radiological examination of the operative specimen and ensuring that the margins are radiologically clear. The MarginProbe will then be used to examine all six outer surfaces of the lumpectomy specimens with five to eight measurements per face..

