A single positive reading identifying a margin as positive: The device output is recorded and Surgeons will be required to excise additional tissue from the corresponding surface of the lumpectomy cavity from every device identifying positive margins.

Additional tissue removed following analysis by the device will not be examined by the device, nor will the lumpectomy cavity. The device should be used within 20 minutes after specimen excision. In both study arms, the main lumpectomy specimens will be orientated and shaves will also be orientated.

Specimens will be interpreted by the Surgeon for the presence and absence of tissue abnormalities registered during surgery and compared to the Pathologists' interpretation of the permanent section pathology slides.

The agreement between the Surgeon's interpretation of MarginProbe positivity and the pathology results will be recorded and the potential reduction of repeat surgery will be assessed by including additional shavings taken and their weight, based on the reading of the device images and the NHS BSP QA reporting of the pathology.

The Pathologists will record tissue dimensions, margin status and margin distance, using micrometer for all surfaces. Specimen volume will be calculated based on the ellipsoid formula (π /6xLxWxD). All patients will be followed (including additional surgical procedures) until the completion of surgical treatment and nine months thereafter.

No restrictions will be placed on Surgeons in terms of performance or additional surgical procedures but additional surgical procedures should be decided by the Breast MDT in the Surgical Units and for the purpose of this study, a positive margin will be considered to be disease less than 1mm from the inked edge of the tissue and diagnostic measures including false-negative and false-positive rates will be evaluated by comparison of device readings so pathology is the gold standard of margin by margin basis.

The molecular phenotype of all tumours will be recorded, to assess whether MarginProbe accuracy is affected by molecular phenotype.

Components:

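### Follow-up is timed from conflicting origins, one of which (the end of surgical treatment) depends on re-excision, the primary outcome

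*Protocol*

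**What the plan says.** **Re-excision endpoint.** Three statements agree. The Summary gives the "number of people requiring second re-excision surgery within 9 months of their first BCS". The first primary objective is set "compared to standard surgical practice by 9 months after primary surgery". Section 4, Primary Endpoints, uses "at least one further surgical re-excision operation by 9 months". The quality-of-life text in Section 3 adds a +3 month window for collecting re-excision details and foresees re-excision after chemotherapy.

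**Two-week statement.** Minimizing loss to follow up (Section 3) says: "The co-primary endpoint data is obtained during the (initial) surgery and during a period of up to two weeks following it". The Background says: "Re-excision procedures occur 5-6 weeks after initial BCS".

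**Questionnaires and diaries.** The Schedule of Assessments has both at 1, 3 and 9 months post-surgery. The objectives and the quality-of-life texts in Sections 3 and 4 give the same times for questionnaires, and the longitudinal analysis in Section 4 counts the same months from randomisation. Minimizing loss to follow up instead gives 1, 6 and 9 months, counted from the end of surgical treatment. The analysis of covariance in Section 4 is at 6 months, for which the Schedule has no visit.

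**Cosmesis.** Cosmetic evaluation in Section 3 rests on pictures "which will be conducted at baseline and 9 months", as do the objectives and the Schedule. Follow up and data collection has the "evaluation of cosmetic status, performed at 6 +/- 1 month following the end of surgical treatment".

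**End of follow-up.** This is that cosmetic visit (Follow up and data collection), or "until the completion of surgical treatment and nine months thereafter" (Trials Procedures, MarginProbe Device), or the Schedule's last column at 9 months post-surgery.

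**The concern.** Primary surgery and randomisation fall on the same day, because women are randomised in theatre. Time counted from that day cannot be changed by allocation. The end of surgical treatment comes after randomisation and is later for any woman who is re-excised, which is the event the device is meant to prevent. Under that clock, assessment time depends on the primary outcome, and the plan expects twice as many delayed women in the control arm.

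Quality of life would be affected most directly. The objectives call it crucial and plan an area-under-the-curve analysis. If the clock restarts at re-excision, the curve leaves out the wait for the second operation, part of the burden the device is meant to remove.

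Two further problems follow. One version of the end of follow-up falls before the primary endpoint is complete. The two-week statement supports the protocol's expectation that loss to follow-up will not affect the co-primary endpoints, yet re-excision happens after those two weeks. The protocol does not say which clock takes precedence, so sites could follow different ones.

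**Working it through.** **Inputs.** Re-excision 25% v 12.5%, 219 per group needed and 230 recruited (Section 4, Sample size). Re-excision 5-6 weeks after first surgery (Background). Cosmetic visit at 6 months, plus or minus 1 (Follow up and data collection). One month = 30.4375/7 = 4.35 weeks.

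**1. The plan's own figure.** Two proportions, 25% v 12.5%, two-sided 5%, 90% power, chi-square with continuity correction: 219 per group, as stated (203 without the correction). The timing problem does not change the sample size.

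**2. Women affected.**
- Control: 0.25 x 230 = 57.5.
- Device: 0.125 x 230 = 28.75.

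**3. Shift for a re-excised woman on the end-of-surgery clock.**
- 1-month questionnaire: 4.35 + 5 = 9.35 to 4.35 + 6 = 10.35 weeks after primary surgery, about 10 weeks.
- 6-month cosmetic visit: 6 + 5/4.35 = 7.15 to 6 + 6/4.35 = 7.38 months.
- 9-month questionnaire: 10.15 to 10.38 months.

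On the Schedule's clock, the 1-month form (4.35 weeks) falls in the wait before re-excision. The 3-month form (13.0 weeks) comes 13 - 6 = 7 to 13 - 5 = 8 weeks after it.

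**4. Mean shift by arm** (re-excision rate x delay).
- Control: 0.25 x 5 = 1.25 to 0.25 x 6 = 1.5 weeks.
- Device: 0.125 x 5 = 0.63 to 0.125 x 6 = 0.75 weeks.
- Difference: 0.63 to 0.75 weeks, or 4.4 to 5.3 days.
- If chemotherapy comes first: the protocol gives neither a frequency nor a delay. Assuming that every re-excision is delayed to 26-39 weeks, the difference is 0.125 x 26 = 3.3 to 0.125 x 39 = 4.9 weeks. This is an upper bound for that assumed delay.
- Clock from primary surgery: difference 0.

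**5. End of follow-up under Follow up and data collection.** The end of surgical treatment is defined there only as conversion to mastectomy or the latest repeat lumpectomy. Women without further surgery (planned 75% v 87.5%) have no stated start. If primary surgery is used for them, follow-up ends at 6 - 1 = 5 to 6 + 1 = 7 months, before 9 months. For a woman re-excised at 5-6 weeks it ends at 5 + 1.15 = 6.15 to 7 + 1.38 = 8.38 months, also before 9.

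**6. Two-week statement.** Five to six weeks lies wholly outside two weeks. Margin status comes from the pathology of the initial operation, so the statement can fit that endpoint. It cannot describe when re-excision data become available.

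**The case against.** The strongest reply is that the main timetable is clear. The objectives, the quality-of-life texts, the Schedule and the analysis section all use 1, 3 and 9 months from surgery or randomisation. The only contrary statement for questionnaires is a paragraph about attrition. Sites that follow the Schedule would have no timing difference by arm, and even on the other clock the mean difference is 4-5 days at 5-6 weeks to re-excision. This stands. The bias is conditional and, on average, small. The shift is nevertheless concentrated in the re-excised women, in whom a quality-of-life effect is expected.

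The choice of anchor for cosmesis is also a genuine trade-off. Counting from the last operation equalises healing time. Counting from primary surgery means that some women are photographed soon after a late re-excision, and more of them would be controls. The protocol needs one stated choice. It does not show that only one anchor is acceptable.

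A reader might infer three stronger points that the documents do not support:
- **That primary data close at two weeks, so that almost no re-excisions are captured.** The statement explains why little attrition is expected and is not a cut-off. The endpoint is put at 9 months in three places, and all ipsilateral procedures are to be recorded.
- **That the end-of-surgery clock misses recovery from re-excision.** One month after re-excision is still within recovery. Only the wait beforehand is lost.
- **That following women for nine months after their last operation biases the re-excision count.** That text sets the length of observation, not the counting window. Any such bias disappears once counting stops at 9 months from primary surgery.

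**Conclusion.** The point holds as a contradiction in timing that needs correcting. The end-of-surgery clocks in Follow up and data collection, Minimizing loss to follow up, and the MarginProbe Device text cannot be reconciled with the Schedule and the endpoint definitions. If followed, they would time assessments by the primary outcome, or end follow-up at 5-7 months for women without further surgery, against an endpoint at 9 months. The second figure assumes that their clock starts at primary surgery, because the protocol gives no start.

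For a woman re-excised at 5-6 weeks the shift is 5-6 weeks. The mean difference between arms is 0.63-0.75 weeks under the planned rates, and larger only to the extent that chemotherapy comes before re-excision. The two-week statement is wrong for re-excision and should not be used to dismiss loss to follow-up for that endpoint. The definition of the re-excision endpoint is otherwise consistent, and the sample size is unaffected.

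**What to change.** - Time quality of life, diaries and the re-excision count from primary surgery (the day of randomisation), at the Schedule's 1, 3 and 9 months.
- Count re-excisions dated within 9 months of primary surgery. State that the +3 months is for collecting records only.
- Follow every woman to at least 9 months from primary surgery, and replace the other two statements of when follow-up ends.
- Limit the two-week statement to margin status.
- Reconcile the 6-month analysis of covariance with the Schedule, which has no 6-month visit.
- State one cosmetic time point. The Schedule's 9 months is the one given most often. Record time since the last operation alongside it.

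The cost is protocol wording, with no change in sample size. The downside is that some photographs will fall soon after a late re-excision, which the recorded time since the last operation would make visible. Assessments made at the wrong time cannot be recovered later.
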